4.5.3.2 Topotecan

Treatment with topotecan should be permanently discontinued for the following:

- Confirmed new diagnosis of interstitial lung disease (ILD): Topotecan has been associated with reports of ILD, some of which have been fatal. Underlying risk factors include history of ILD, pulmonary fibrosis, lung cancer, thoracic exposure to radiation, and use of pneumotoxic drugs and/or colony stimulating factors. Monitor subjects for pulmonary symptoms indicative of interstitial lung disease (eg, cough, fever, dyspnea, and/or hypoxia), and discontinue topotecan if a new diagnosis of ILD is confirmed.
- Any dosing interruption lasting > 6 weeks (42 days) from the last dose.
- Any AE, laboratory abnormality, or intercurrent illness which, in the judgment of the Investigator, presents a substantial clinical risk to the subject with continued topotecan dosing.
- Any dosing interruption lasting > 6 weeks from the last dose with the following exception:
 - Dosing interruptions > 6 weeks from the last dose that occur for non-drug-related reasons may be allowed if approved by the BMS Medical Monitor.

Tumor assessments for all subjects should continue as per protocol even if study drug dosing is delayed.

4.5.3.3 Amrubicin

Treatment with amrubicin should be permanently discontinued for the following:

- Confirmed new diagnosis of interstitial lung disease (ILD): Amrubicin has been associated with reports of ILD, some of which have been fatal. Underlying risk factors include history of ILD, pulmonary fibrosis, lung cancer, thoracic exposure to radiation, and use of pneumotoxic drugs and/or colony stimulating factors. Monitor subjects for pulmonary symptoms indicative of interstitial lung disease (eg, cough, fever, dyspnea, and/or hypoxia), and discontinue topotecan if a new diagnosis of ILD is confirmed
- Any dosing interruption lasting > 6 weeks (42 days) from the last dose.
- Any AE, laboratory abnormality, or intercurrent illness which, in the judgment of the Investigator, presents a substantial clinical risk to the subject with continued amrubicin dosing.
- Any dosing interruption lasting > 6 weeks from the last dose with the following exception:
 - Dosing interruptions > 6 weeks from the last dose that occur for non-drug-related reasons may be allowed if approved by the BMS Medical Monitor.

Tumor assessments for all subjects should continue as per protocol even if study drug dosing is delayed.

4.5.4 Treatment Beyond Disease Progression

Accumulating evidence indicates a minority of subjects treated with immunotherapy may derive clinical benefit despite initial evidence of PD.²²

Subjects in Arm B who were treated with topotecan or amrubicin will not be permitted to continue treatment beyond RECIST 1.1 defined initial PD.

Subjects in Arm A who were treated with Nivolumab will be permitted to continue treatment beyond initial RECIST 1.1 defined PD as long as they meet the following criteria:

- Investigator-assessed clinical benefit and no rapid disease progression
- Tolerating study drug
- Stable performance status
- Treatment beyond progression will not delay an imminent intervention to prevent serious complications of disease progression (eg, CNS metastases)
- Provides written informed consent prior to receiving additional nivolumab treatment, using an ICF describing any reasonably foreseeable risks or discomforts, or other alternative treatment options.

The assessment of clinical benefit should be balanced by clinical judgment as to whether the subject is clinically deteriorating and unlikely to receive any benefit from continued treatment with nivolumab.

All decisions to continue treatment beyond initial progression must be discussed with the BMS Medical Monitor and documented in the study records. The subject will continue to receive monitoring according to the Time and Events Schedule on [Table 5.1-2](#).

A radiographic assessment/ scan should be performed within 6 weeks of original PD to determine whether there has been a decrease in the tumor size, or continued PD.

For the subjects who continue nivolumab study therapy beyond progression, further progression is defined as an additional 10% increase in tumor burden volume from time of initial PD. This includes an increase in the sum of all target lesions and/ or the development of new measurable lesions. For subjects with evaluable disease only, further progression is defined as unequivocal disease progression of non target lesions or the development of new measurable lesions from time of initial PD. Treatment should be discontinued permanently upon documentation of further disease progression.

New lesions are considered measurable at the time of initial progression if the longest diameter is at least 10 mm (except for pathological lymph nodes, which must have a short axis of at least 15 mm). Any new lesion considered non-measurable at the time of initial progression may become measurable and therefore included in the tumor burden measurement if the longest diameter increases to at least 10 mm (except for pathological lymph nodes, which must have an increase in short axis to at least 15 mm).

For statistical analyses that include the investigator-assessed progression date, subjects who continue treatment beyond initial investigator-assessed, RECIST 1.1-defined progression will be considered to have investigator-assessed progressive disease at the time of the initial progression event.

For subjects in both treatment arms, global deterioration of health status requiring discontinuation of treatment without objective evidence of disease progression at that time should be reported as ‘symptomatic deterioration’. Every effort should be made to document objective progression (ie radiographic confirmation) even after discontinuation of treatment.

4.5.5 Treatment of Nivolumab-related Infusion Reactions

Since nivolumab contains only human immunoglobulin protein sequences, it is unlikely to be immunogenic and induce infusion or hypersensitivity reactions. However, if such a reaction were to occur, it might manifest with fever, chills, rigors, headache, rash, pruritus, arthralgias, hypo- or hypertension, bronchospasm, or other symptoms. All Grade 3 or 4 infusion reactions should be reported within 24 hours to the BMS Medical Monitor and reported as a serious adverse event (SAE) if criteria are met. Infusion reactions should be graded according to NCI CTCAE (version 4.0) guidelines.

Treatment recommendations are provided below and may be modified based on local treatment standards and guidelines as appropriate:

For Grade 1 symptoms: (Mild reaction; infusion interruption not indicated; intervention not indicated)

- Remain at bedside and monitor subject until recovery from symptoms. The following prophylactic premedications are recommended for future infusions: diphenhydramine 50 mg (or equivalent) and/or paracetamol 325 to 1000 mg (acetaminophen) at least 30 minutes before additional nivolumab administrations.

For Grade 2 symptoms: (Moderate reaction requires therapy or infusion interruption but responds promptly to symptomatic treatment [eg, antihistamines, non-steroidal anti inflammatory drugs, narcotics, corticosteroids, bronchodilators, IV fluids]; prophylactic medications indicated for ≤ 24 hours).

- Stop the nivolumab infusion, begin an IV infusion of normal saline, and treat the subject with diphenhydramine 50 mg IV (or equivalent) and/or paracetamol 325 to 1000 mg (acetaminophen); remain at bedside and monitor subject until resolution of symptoms. Corticosteroid or bronchodilator therapy may also be administered as appropriate. If the infusion is interrupted, then restart the infusion at 50% of the original infusion rate when symptoms resolve; if no further complications ensue after 30 minutes, the rate may be increased to 100% of the original infusion rate. Monitor subject closely. If symptoms recur then no further nivolumab will be administered at that visit. Administer diphenhydramine 50 mg IV, and remain at bedside and monitor the subject until resolution of symptoms. The amount of study drug infused must be recorded on the case report form (CRF).
- The following prophylactic premedications are recommended for future infusions: diphenhydramine 50 mg (or equivalent) and/or paracetamol 325 to 1000 mg (acetaminophen) should be administered at least 30 minutes before additional nivolumab administrations. If necessary, corticosteroids (recommended dose: up to 25 mg of IV hydrocortisone or equivalent) may be used.

For Grade 3 or Grade 4 symptoms: (Severe reaction, Grade 3: prolonged [ie, not rapidly responsive to symptomatic medication and/or brief interruption of infusion]; recurrence of symptoms following initial improvement; hospitalization indicated for other clinical sequelae [eg, renal impairment, pulmonary infiltrates]). Grade 4: (life threatening; pressor or ventilatory support indicated).

- Immediately discontinue infusion of nivolumab. Begin an IV infusion of normal saline, and treat the subject as follows. Recommend bronchodilators, epinephrine 0.2 to 1 mg of a 1:1,000 solution for subcutaneous administration or 0.1 to 0.25 mg of a 1:10,000 solution injected slowly for IV administration, and/or diphenhydramine 50 mg IV with methylprednisolone 100 mg IV (or equivalent), as needed. Subject should be monitored until the investigator is comfortable that the symptoms will not recur. Nivolumab will be permanently discontinued. Investigators should follow their institutional guidelines for the treatment of anaphylaxis. Remain at bedside and monitor subject until recovery from symptoms.

In the case of late-occurring hypersensitivity symptoms (eg, appearance of a localized or generalized pruritus within 1 week after treatment), symptomatic treatment may be given (eg, oral antihistamine, or corticosteroids)

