4.5.3 Discontinuation Criteria

4.5.3.1 Nivolumab

Treatment with nivolumab should be permanently discontinued for the following:

- Grade 2 drug-related uveitis, eye pain or blurred vision that does not respond to topical therapy and does not improve to Grade 1 severity within the re-treatment period OR requires systemic treatment
- Grade 3 non-skin, drug-related adverse event lasting > 7 days or recurs, with the following exceptions for laboratory abnormalities, drug related uveitis, pneumonitis, bronchospasm, neurologic toxicity, hypersensitivity reactions, infusion reactions and endocrinopathies:
 - Grade 3 drug-related uveitis, pneumonitis, bronchospasm, neurologic toxicity, myocarditis, hypersensitivity reaction, or infusion reaction of any duration require discontinuation
 - Grade 3 drug-related endocrinopathies adequately controlled with only physiologic hormone replacement do not require discontinuation; Adrenal insufficiency requires discontinuation regardless of control with hormone replacement.
 - Grade 3 drug-related laboratory abnormalities do not require treatment discontinuation except:
 - ◆ Grade 3 drug-related thrombocytopenia > 7 days or associated with bleeding requires discontinuation
 - ◆ Grade ≥ 3 drug-related AST, ALT or Total Bilirubin requires discontinuation*
 - ◆ Concurrent AST or ALT > 3 x ULN and total bilirubin > 2x ULN
- * In most cases of Grade 3 AST or ALT elevation, study drug(s) will be permanently discontinued. If the investigator determines a possible favorable benefit/risk ratio that warrants continuation of study drug(s), a discussion between the investigator and the BMS Medical Monitor/designee must occur
- Any Grade 4 drug-related adverse event or laboratory abnormality (including but not limited to creatinine, AST, ALT, or Total Bilirubin) except for the following events which do not require discontinuation:
 - Grade 4 neutropenia ≤ 7 days
 - Grade 4 lymphopenia or leukopenia or asymptomatic amylase or lipase
 - Isolated Grade 4 electrolyte imbalances/abnormalities that are not associated with clinical sequelae and are corrected with supplementation/appropriate management within 72 hours of their onset
 - Grade 4 drug-related endocrinopathy adverse events, such as hyper- or hypothyroidism, or glucose intolerance, which resolve or are adequately controlled with physiologic hormone replacement (corticosteroids, thyroid hormones) or glucose-controlling agents,

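### Section 4.5.5 gives incompatible instructions for a nivolumab infusion reaction that resolves, is restarted at half rate and then recurs: the Grade 2 branch stops dosing for that visit only, while the Grade 3 definition leads to permanent discontinuation

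*Protocol*

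**What the plan says.** Three pieces of Protocol text bear on the same clinical course.

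- **Section 4.5.5, Grade 2 symptoms.** The infusion is stopped and symptoms are treated. If the infusion was interrupted, the site is to "restart the infusion at 50% of the original infusion rate when symptoms resolve". On recurrence: "If symptoms recur then no further nivolumab will be administered at that visit". The next bullet under Grade 2 opens "The following prophylactic premedications are recommended for future infusions" and says that these drugs "should be administered at least 30 minutes before additional nivolumab administrations".
- **Section 4.5.5, Grade 3 or Grade 4 symptoms.** The description of a Grade 3 reaction includes "recurrence of symptoms following initial improvement". The instruction for this branch is "Nivolumab will be permanently discontinued".
- **Section 4.5.3.1, discontinuation criteria for nivolumab.** Among Grade 3 drug-related events, "neurologic toxicity, myocarditis, hypersensitivity reaction, or infusion reaction of any duration require discontinuation".

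The opening paragraph of Section 4.5.5 adds three general rules. Infusion reactions are graded by NCI CTCAE version 4.0. Grade 3 and 4 reactions go to the Medical Monitor within 24 hours, and are also reported as SAEs if they meet the SAE criteria. The treatment recommendations may be adapted to local standards.

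**The concern.** The Grade 2 branch plans for recurrence after a restart and treats it as an event within Grade 2, with consequences limited to that visit. The Grade 3 definition appears to claim the same event and attaches permanent discontinuation to it. A site that follows one sentence may re-dose a subject whom another sentence requires to stop. A site that follows the other takes a subject off study drug although the Grade 2 text anticipates further infusions.

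The chosen grade also decides whether the Medical Monitor must be told within 24 hours when the reaction is not serious. It fixes the grade that enters the safety tables too, because Section 8.4.3 tabulates adverse events by worst CTCAE grade.

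**Working it through.** The plan states no figure to reproduce on this point. The check is to follow one subject through the text, then to estimate how many subjects could be affected.

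**Tracing one subject**

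1. A moderate reaction occurs and the infusion is interrupted. This is the Grade 2 description in Section 4.5.5.
2. Symptoms resolve and the infusion restarts at half rate. The restart is conditional on resolution, so initial improvement has occurred by construction.
3. Symptoms return.

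At step 3 the texts diverge:

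| Question | Grade 2 branch, 4.5.5 | Grade 3 branch, 4.5.5, and 4.5.3.1 |
|---|---|---|
| Does the text describe this course? | Yes, it names recurrence after restart | Yes, it names recurrence after initial improvement |
| Nivolumab at this visit | No more | Infusion stopped |
| Nivolumab at later visits | Expected, with premedication | None; permanently discontinued |
| 24-hour notice to the Medical Monitor if not an SAE | Not required by this section | Required |

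The recurrence wording in the Grade 3 definition is a separate element, set off by a semicolon from the item after it: "recurrence of symptoms following initial improvement; hospitalization indicated for other clinical sequelae". Nothing limits it to recurrence without re-exposure, and nothing exempts recurrence on restart. The two branches agree on the current visit and conflict on every later one.

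**How many subjects**

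Inputs:

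- Arm A size: 560 randomized 1:1 (Section 8.1), so 560 / 2 = 280.
- Lower reaction rate: 1.9% hypersensitivity or infusion reactions in CA209037, at 3 mg/kg (Section 1.1.3.3).
- Upper reaction rate: 3.7% at 2 mg/kg in CA209010 (Section 1.1.7).
- Share recurring after restart: not in the documents; 10% to 30% is assumed.

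Expected reactions = Arm A size × rate:

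- 280 × 0.019 = 5.3
- 280 × 0.037 = 10.4

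This is about 5 to 10 reactions. Expected recurrences = reactions × share:

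- low: 5 × 0.10 = 0.5
- high: 10 × 0.30 = 3

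As a proportion of Arm A, 0.5 / 280 = 0.2% and 3 / 280 = 1.1%.

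The range is rough. The reaction counts include Grade 1 events, for which Section 4.5.5 does not call for interruption and which therefore cannot recur after a restart. The CA209010 rate covers infusion site and hypersensitivity reactions, all Grade 1 or 2. Section 1.1.7 says that earlier monotherapy studies used 60-minute infusions, against 30 minutes here. Severe reactions do occur in this disease: Section 1.1.3.2 reports one Grade 3/4 infusion-related reaction among 40 nivolumab-treated SCLC subjects.

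**The case against.** The strongest defence is that the sentences can be followed together. The Grade 2 recurrence sentence governs only the current visit and does not itself promise another dose. The premedication bullet concerns Grade 2 reactions in general and does not mention recurrence. A site could stop for the visit, grade the event by CTCAE, find that it meets the printed Grade 3 definition, and apply Section 4.5.3.1. On this view the bedside steps are only recommendations, Section 4.5.3.1 is the binding rule, and just a cross-reference is missing.

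Part of this stands: the protocol does name a grading scale, and Section 4.5.3.1 carries no allowance for local modification. But the reading strips the limit to one visit, and the premedication bullet after it, of their natural meaning. If recurrence always meant permanent discontinuation, there would be no reason to confine the instruction to that visit or to place it under Grade 2. Neither the CTCAE sentence nor the local-adaptation sentence says which branch governs.

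A reader might also infer more than the documents support:

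- *That acute drug treatment conflicts, with diphenhydramine alone under Grade 2.* The Grade 2 bullet also allows corticosteroids or bronchodilators, and the Grade 3/4 list also includes diphenhydramine. Of the drug types listed, only epinephrine is confined to the Grade 3/4 branch.
- *That all 24-hour reporting depends on the grade.* Section 6.1.1 requires SAEs of any grade to be reported within 24 hours. Only the Medical Monitor notice for a non-serious reaction turns on the grade.
- *That some 52 subjects could have a reaction.* That is 280 × 18.5% = 51.8, using the CA209010 rate at 10 mg/kg. The trial dose of 240 mg equals 3 mg/kg at 80 kg (Section 1.1.6).
- *That the Arm A safety results hinge on how sites read the section.* At most about 3 of 280 subjects are involved under the assumptions above, and safety is summarized descriptively.

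**Conclusion.** The contradiction is real and rests on the protocol's own wording. For a reaction that resolves, is restarted at half rate and recurs, Section 4.5.5 supports both continued dosing with premedication and permanent discontinuation, and Section 4.5.3.1 reinforces the second without addressing the first. Medical Monitor notification of a non-serious event is unclear for the same reason.

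The likely number affected is small: about 0.5 to 3 Arm A subjects, given 5 to 10 reactions and the assumed 10% to 30% recurrence share. The textual finding does not depend on that estimate. Overall survival, sample size, power and type I error are unaffected. The point merits correction because the conflict arises in an acute safety situation and concerns whether a subject is re-exposed, not because of its frequency.

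**What to change.** Reconcile three places in a protocol amendment: the Grade 2 recurrence sentence and its premedication bullet in Section 4.5.5, the Grade 3 definition in the same section, and the Grade 3 infusion-reaction rule in Section 4.5.3.1. State once which grade applies when symptoms recur after the infusion is restarted, and let later dosing or discontinuation and the 24-hour Medical Monitor notice follow from that grade. Which clinical rule is right is for the sponsor's medical team, and this review takes no position on it.

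The cost is a short wording change, ethics committee review of the amendment and notification of sites. No data collection, sample size or analysis changes. An administrative letter may look sufficient, and Section 9.1.1 mentions that route. But the same section requires ethics approval of an amendment before a protocol change is implemented, except for an immediate hazard, and a sentence that decides when study drug is permanently stopped is better handled as an amendment.

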4.6 Blinding/Unblinding

Not applicable.

4.7 Treatment Compliance

Treatment compliance will be monitored by drug accountability as well as the subject's medical record and CRF.

4.8 Destruction of Study Drug

For this study, study drugs (those supplied by BMS or sourced by the investigator) such as partially used study drug containers, vials and syringes may be destroyed on site.

Any unused study drugs can only be destroyed after being inspected and reconciled by the responsible Study Monitor unless study drug containers must be immediately destroyed as required for safety, or to meet local regulations (eg, cytotoxics or biologics).

On-site destruction is allowed provided the following minimal standards are met:

- On-site disposal practices must not expose humans to risks from the drug.
- On-site disposal practices and procedures are in agreement with applicable laws and regulations, including any special requirements for controlled or hazardous substances.
- Written procedures for on-site disposal are available and followed. The procedures must be filed with the site's SOPs and a copy provided to BMS upon request.
- Records are maintained that allow for traceability of each container, including the date disposed of, quantity disposed, and identification of the person disposing the containers. The method of disposal, ie, incinerator, licensed sanitary landfill, or licensed waste disposal vendor must be documented.
- Accountability and disposal records are complete, up-to-date, and available for the Monitor to review throughout the clinical trial period.

If conditions for destruction cannot be met the responsible Study Monitor will make arrangements for return of study drug.

It is the investigator's responsibility to arrange for disposal of all empty containers, provided that procedures for proper disposal have been established according to applicable federal, state, local, and institutional guidelines and procedures, and provided that appropriate records of disposal are kept.

4.9 Return of Study Drug

If study drug will not be destroyed upon completion or termination of the study, all unused and/or partially used study drug that was supplied by BMS must be returned to BMS. The return of study drug will be arranged by the responsible Study Monitor.

It is the investigator's responsibility to arrange for disposal of all empty containers, provided that procedures for proper disposal have been established according to applicable federal, state, local, and institutional guidelines and procedures, and provided that appropriate records of disposal are kept.

5 STUDY ASSESSMENTS AND PROCEDURES

5.1 Flow Chart/Time and Events Schedule

Table 5.1-1: Screening Procedural Outline (CA209331)

| Procedure | Screening Visit | Notes |
|---------------------------------------|-----------------|--|
| Eligibility Assessments | | |
| Informed Consent | X | |
| Inclusion/Exclusion Criteria | X | All inclusion/exclusion criteria should be assessed at screening and confirmed prior to first dose |
| Medical History | X | |
| Prior Systemic Therapy | X | |
| Safety Assessments | | |
| Physical Examination | X | |
| Physical Measurements | X | Include Height, Weight, and ECOG performance Status. Within 14 days prior to first dose |
| Vital Signs and Oxygen Saturation | X | Temperature, BP, HR, and O2 saturation by pulse oximetry at rest. Obtain vital signs at the screening visit and within 72 hours prior to first dose. |
| Assessment of Signs and Symptoms | X | Within 14 days prior to first dose |
| Concomitant Medication Collection | X | Within 14 days prior to first dose |
| Laboratory Tests | X | CBC with differential, Chemistry panel including LDH, AST, ALT, ALP, T.Bili, BUN or serum urea level, uric acid, creatinine, Ca, Mg, Na, K, Cl, P, glucose, bicarbonates (optional), albumin, amylase or lipase, TSH (reflex to free T3, free T4 for abnormal TSH result), hepatitis B surface antigen (HBVsAg), and hepatitis C antibody (HCV Ab) or hepatitis C RNA (HCV RNA), within 14 days prior to first dose. Screening labs done within 72 hours prior to first dose can also be used for on treatment lab purposes at Day 1 dosing. |
| ECG, Echocardiogram (LVEF) or MUGA | X | |

Table 5.1-1: Screening Procedural Outline (CA209331)

| Procedure | Screening Visit | Notes |
|---|-----------------|--|
| Pregnancy Test | X | Performed within 24 hours prior to first dose for WOCBP only (serum or urine - local/site) |
| Efficacy/Biomarker Assessments | | |
| Radiographic Tumor Assessment | X | Contrast-enhanced CT of the chest and CT or MRI of abdomen, pelvis, and any other known sites of disease. Brain MRI or CT. Subjects with incidental brain metastases findings at screening will need to undergo radiation treatment first to be eligible. Should be performed within 28 days prior to randomization. Additional sites of known or suspected disease (including CNS) should be imaged at the screening visit and at subsequent on-study assessments. |
| Collection of Tumor Tissue for Biomarker Evaluation | X | Tumor tissue obtained before randomization (formalin-fixed, paraffin-embedded (FFPE) tumor tissue block or minimum of 10 slides, obtained from core biopsy, punch biopsy, excisional biopsy or surgical specimen). Fine needle aspiration or cytospins are insufficient. For subjects where a biopsy is not feasible, archival tumor material must be made available. Submission of fewer than 10 unstained slides may be accepted under certain circumstances and must be approved by BMS medical monitor Specimens must be received by the central lab prior to subject randomization. |
| IVRS/Clinical Drug Supplies | | |
| Phone Calls to IVRS | X | Phone calls must be made to IVRS as follows: For subject number assignment at the time informed consent is obtained. For randomization to treatment after eligibility has been confirmed, or in the event of screen failure (subject does not meet eligibility criteria). |

ALP = alkaline phosphatase, ALT = alanine aminotransferase, AST = aspartate aminotransferase, BP = blood pressure, BUN = blood urea nitrogen, Ca = calcium, CBC = complete blood count, Cl = chloride, CNS = central nervous system, CT = computed tomography, ECOG = Eastern Cooperative Oncology Group, HR = heart rate, IVRS = interactive voice response system, K = potassium, LDH = lactate dehydrogenase, Mg = magnesium, MRI = magnetic resonance imaging, Na = sodium, O2 = oxygen, P = phosphorus, T.Bili = total bilirubin, TSH = thyroid stimulating hormone, T3 = triiodothyronine, T4 = thyroxine, WOCBP = women of childbearing potential

Table 5.1-2: On-Treatment Assessments for Subjects Randomized to Arm A, Nivolumab Monotherapy (CA209331)

| Procedure | Cycle 1 Day 1 (C1D1) | Cycle 1 Day 8 (C1D8) | Each Cycle (Every 2 Weeks) on Day 1 (± 3 Days) | Notes |
|-----------------------------------|------------------------|----------------------|---|---|
| Safety Assessments | | | | |
| Targeted Physical Examination | X | | X | Within 72 hours prior to dosing |
| Vital Signs and Oxygen Saturation | X | | X | Temperature, BP, HR, O2 saturation by pulse oximetry at rest (also monitor amount of supplemental oxygen if applicable) within 72 hours prior to dosing and at any time a subject has any new or worsening respiratory symptoms |
| Physical Measurements | X | | X | Includes Weight and ECOG performance status |
| Adverse Events Assessment | -----Continuously----- | | | Assessed using NCI CTCAE v. 4.0. SAEs should be approved in Trial Access Online (TAO) within 5 days from entry |
| Review of Concomitant Medications | X | | X | |
| Laboratory Tests | X | | X | Extended on-study local laboratory assessments should be done within 72 hours prior to dosing for Cycle 1 through Cycle 5 and every alternate dose thereafter (Cycles 7, 9, 11, 13, etc.) and include: CBC with differential, uric acid, serum urea level, creatinine, Na, K, Ca, Mg, phosphorus, chloride, bicarbonate (optional), amylase or lipase, glucose, AST, ALT, total bilirubin, alkaline phosphatase, LDH. Limited on-study local laboratory assessment should be done within 72 hours prior to dosing (beginning at Cycle 6 and every alternate dose thereafter (Cycles 8, 10, 12, 14, etc.) and include: CBC with differential, LFTs (ALT, AST, t.bili, alkaline phosphatase) and creatinine. |
| Thyroid Function Testing | | | See Note | TSH (reflex to free T3 and free T4 if abnormal result) to be performed every 6 weeks (± 1 week). |

Table 5.1-2: On-Treatment Assessments for Subjects Randomized to Arm A, Nivolumab Monotherapy (CA209331)

| Procedure | Cycle 1 Day 1 (C1D1) | Cycle 1 Day 8 (C1D8) | Each Cycle (Every 2 Weeks) on Day 1 (\pm 3 Days) | Notes |
|---|----------------------|----------------------|---|--|
| Pregnancy Test | X | | See Note | For WOCBP only: Serum or urine within 24 hours prior to first dose and then at least once every 4 weeks regardless of dosing schedule. |
| Efficacy Assessments | | | | |
| Radiographic Tumor Assessment | | | See Note | CT of the chest. CT/MRI of abdomen and any other known sites of disease. Repeat CT/MRI of pelvis is required for subjects with pelvic metastases at baseline, or if clinically indicated. Subjects with a history of brain metastasis should have surveillance MRI every 6 weeks, or sooner if clinically indicated. The same methods should be used throughout the study. See Table 5.4-1 for CT/MRI scan schedule. |
| Pharmacokinetic (PK) and Immunogenicity Assessments | | | | |
| PK samples | X | | See Note | See Table 5.5-1 of PK and Immunogenicity Sampling |
| Immunogenicity samples | X | | See Note | See Table 5.5-1 of PK and Immunogenicity Sampling |

Table 5.1-2: On-Treatment Assessments for Subjects Randomized to Arm A, Nivolumab Monotherapy (CA209331)

| Procedure | Cycle 1 Day 1 (C1D1) | Cycle 1 Day 8 (C1D8) | Each Cycle (Every 2 Weeks) on Day 1 (± 3 Days) | Notes |
|---|----------------------|----------------------|--|---|
| Exploratory Biomarker Assessments | | | | |
| Biomarker samples (██████, Whole Blood, Tumor Biopsy) | X | X | See Note | See Table 5.6-1 of Biomarker Sampling Schedule |
| Outcomes Research Assessments | | | | |
| Patient Reported Outcomes (PRO) | X | | See Note | For on-study visits: Assessments (Lung Cancer Symptom Scale and EQ-5D) will be performed prior to treatment. Assessments will be performed at each cycle on Day 1 for the first 6 months on study, then every 6 weeks thereafter for the remainder of the treatment phase. |
| Health Resource Utilization | | | X | Except Cycle 1. Note that concomitant medication collection will be included. |
| Study Drug | | | | |
| Administer Study Drug | X | | X | IVRS should be called within 1 day prior to study drug administration to receive vial assignment. Note: Treatment should begin within 3 business days of randomization. Subjects may be dosed no less than 12 days between doses and no more than 3 days from the scheduled dose. IVRS should also be contacted at upon discontinuation of treatment. |

ALP = alkaline phosphatase, ALT = alanine aminotransferase, AST = aspartate aminotransferase, BP = blood pressure, BUN = blood urea nitrogen, Ca = calcium, Cl = chloride, CNS = central nervous system, CT = computed tomography, ECG = electrocardiogram, ECOG = Eastern Cooperative Oncology Group, HR = heart rate, IVRS = interactive voice response system, K = potassium, LDH = lactate dehydrogenase, LFT = liver function tests, Mg = magnesium, MRI = magnetic resonance imaging, Na = sodium, NCI CTCAE = National Cancer Institute Common Toxicity Criteria for Adverse Events, O2 = oxygen, P = phosphorus, SAE = serious adverse event, T.Bili = total bilirubin, TSH = thyroid stimulating hormone, T3 = triiodothyronine, T4 = thyroxine, WOCBP = women of childbearing potential

Table 5.1-3: On-Treatment Assessments for Subjects Randomized to Arm B, Chemotherapy (CA209331)

| Procedure | Cycle 1 Day 1 of a 21-day Cycle (Every 3 Weeks ± 3 Days) (C1D1) | Cycle 2 to x Day 1 of a 21-day Cycle (Every 3 Weeks ± 3 Days) C2D1 to CxD1 | Notes |
|-----------------------------------|---|--|--|
| Safety Assessments | | | |
| Targeted Physical Examination | X | X | Within 72 hours prior to dosing |
| Vital Signs and Oxygen Saturation | X | X | Temperature, BP, HR, O2 saturation by pulse oximetry at rest (also monitor amount of supplemental oxygen if applicable) prior to dosing and at any time a subject has any new or worsening respiratory symptoms |
| Physical Measurements | X | X | Includes Weight and ECOG performance status |
| Adverse Events Assessment | ----- Continuously ----- | | Assessed using NCI CTCAE v. 4.0. SAEs should be approved in Trial Access Online (TAO) within 5 days from entry |
| Review of Concomitant Medications | X | X | |
| Laboratory Tests | X (See Note) | X (See Note) | Extended on-study local laboratory assessments should be done within 72 hours prior to dosing and include: CBC with differential, uric acid, serum urea level, serum creatinine, sodium, potassium, calcium, magnesium, phosphorus, chloride, bicarbonate (optional), amylase or lipase, glucose, AST, ALT, total bilirubin, alkaline phosphatase, LDH. In addition, the following laboratory assessments should be done: Day 15 of each cycle (optional according to local treatment guidelines): CBC with Differential, LFTs (ALT, AST, total bilirubin, alkaline phosphatase) and creatinine. |
| Thyroid Function Testing | | See Note | TSH (reflex to free T3 and free T4 if abnormal result) to be performed every 6 weeks (± 1 week). |
| Pregnancy Test | X | See Note | For WOCBP only: Serum or urine within 24 hours prior to first dose and then at least once every 4 weeks regardless of dosing schedule. |

Table 5.1-3: On-Treatment Assessments for Subjects Randomized to Arm B, Chemotherapy (CA209331)

| Procedure | Cycle 1 Day 1 of a 21-day Cycle (Every 3 Weeks ± 3 Days) (C1D1) | Cycle 2 to x Day 1 of a 21-day Cycle (Every 3 Weeks ± 3 Days) C2D1 to CxD1 | Notes |
|--|---|--|--|
| Efficacy Assessments | | | |
| Radiographic Tumor Assessment | | See Note | CT of the chest. CT/MRI of abdomen and any other known sites of disease. Repeat CT/MRI of pelvis is required for subjects with pelvic metastases at baseline, or if clinically indicated. Subjects with a history of brain metastasis should have surveillance by MRI every 6 weeks or sooner if clinically indicated. The same methods should be used throughout the study. See Table 5.4-1 for schedule of CT/MRI assessments. |
| Exploratory Biomarker Assessments | | | |
| 

 Whole Blood Tumor Biopsy | X | See Note | See Table 5.6-2 of Biomarker Sampling Schedule |
| Outcomes Research Assessments | | | |
| Patient Reported Outcomes (PRO) | X | See Note | For on-study visits: Assessments (Lung Cancer Symptom Scale and EQ-5D) will be performed prior to treatment. Assessments will be performed at each cycle on Day 1 for the first 6 months on study, then every 6 weeks thereafter for the remainder of the treatment period. |
| Health Resource Utilization | | X | Except Cycle 1. Note that concomitant medication collection will be included. |

Table 5.1-3: On-Treatment Assessments for Subjects Randomized to Arm B, Chemotherapy (CA209331)

| Procedure | Cycle 1 Day 1 of a 21-day Cycle (Every 3 Weeks ± 3 Days) (C1D1) | Cycle 2 to x Day 1 of a 21-day Cycle (Every 3 Weeks ± 3 Days) C2D1 to CxD1 | Notes |
|-----------------------|---|--|--|
| Study Drug | | | |
| Administer Study Drug | X (See Note) | X (See Note) | Topotecan: 1.5 mg/m ² administered as 30-minute IV infusion or 2.3 mg/m ² oral capsule (round dose to nearest 0.25 mg) once daily on Days 1 to 5 of a 21-day cycle. Amrubicin (upon investigator’s choice, where locally approved for 2nd line SCLC treatment): 40 mg/m ² administered as 5-minute IV infusion once daily on Days 1 to 3 of a 21-day cycle. IVRS should be called within 1 day prior to study drug administration to receive vial assignment. Note: Treatment should begin within 3 business days of randomization. Subjects assigned to topotecan may be dosed no less than 14 days between doses and no more than 3 days from the scheduled dose. Subjects assigned to amrubicin may be dosed no less than 16 days between doses and no more than 3 days from the scheduled dose. |

ALP = alkaline phosphatase, ALT = alanine aminotransferase, AST = aspartate aminotransferase, BP = blood pressure, BUN = blood urea nitrogen, Ca = calcium, Cl = chloride, CNS = central nervous system, CT = computed tomography, ECG = electrocardiogram, ECOG = Eastern Cooperative Oncology Group, HR = heart rate, IVRS = interactive voice response system, K = potassium, LDH = lactate dehydrogenase, LFT = liver function tests, Mg = magnesium, MRI = magnetic resonance imaging, Na = sodium, NCI CTCAE = National Cancer Institute Common Toxicity Criteria for Adverse Events, O2 = oxygen, P = phosphorus, SAE = serious adverse event, T.Bili = total bilirubin, TSH = thyroid stimulating hormone, T3 = triiodothyronine, T4 = thyroxine, WOCBP = women of childbearing potential

| Table 5.1-4: Follow-Up Assessments for All Treatment Groups (CA209331) | | | |
|---|--|---|---|
| Procedure | X, Follow-Up Visits 1 and 2^a | S, Survival Follow-Up Visits^b | Notes |
| Safety Assessments | | | |
| Targeted Physical Examination | X | | To assess for potential late emergent study drug related issues |
| Adverse Events Assessment | X | X | Non-SAEs and SAEs must be collected up to 100 days after study drug discontinuation. SAEs that relate to any later protocol specified procedure must be collected. SAEs should be approved in Trial Access Online (TAO) within 5 days from entry. |
| Review concomitant medications | X | | This includes subsequent cancer therapy and concomitant medication taken up to 100 days after study drug discontinuation |
| Laboratory Tests | X | | CBC with differential, uric acid, BUN, serum creatinine, Na, K, Ca, Mg, Cl, P, bicarbonate (optional), glucose, AST, ALT, t.bili, ALP, LDH. |
| Thyroid Function Testing | X | | TSH (reflex to free T3 and free T4 if abnormal result) |
| Pregnancy Test | X | | Serum or urine |
| ECG, Echocardiogram (LVEF) or MUGA | X | | Only at Follow-up Visit 1 |
| Efficacy Assessments | | | |
| Radiographic Tumor Assessment | See Note | See note | See Table 5.4-1 for schedule of CT/MRI assessments. For subjects without previous disease progression only. |
| Exploratory Biomarker Assessments | | | |
| Biomarker samples (■■■■), whole | See Note | See note | Collection of Biomarker samples at time of |

| Table 5.1-4: Follow-Up Assessments for All Treatment Groups (CA209331) | | | |
|---|--|---|--|
| Procedure | X, Follow-Up Visits 1 and 2^a | S, Survival Follow-Up Visits^b | Notes |
